4.4 Determination of Sample Size

No power or sample size calculation was done for this exploratory study. Twenty-three (23) subjects were dosed with flortaucipir and had an accompanying visual read or imaging quantification.

5 CHANGES IN THE CONDUCT OF THE STUDY OR PLANNED ANALYSES

5.1 Changes in the Conduct of the Study

There were no changes in the conduct of the study at the time of preparing this statistical analysis plan (SAP).

6 BASELINE, EFFICACY AND SAFETY EVALUATIONS

6.1 Schedule of Evaluations

Evaluations	Screening Assessments ^a	¹⁸ F-AV- 1451 Imaging Visit	End of ¹⁸ F-AV- 1451 Imaging (prior to discharge)	Follow-up Phone Call ^b
Signed Informed Consent	X			
Demographics	X			
Medical History	X			
Concomitant Medications	X			
ECG	X ^c			
PET Brain Scan		X ^{d, e}		
Evaluation by a physician	X	X ^f	X ^g	
Pregnancy Test	X ^h	X ⁱ		
Adverse Events	X	X	X	X
Serious Adverse Events	X	X	X	X

- a. Screening may take place over several days. All assessments must be performed within 90 days prior to the flortaucipir (¹⁸F) imaging session. Subjects may be permitted to return for the flortaucipir (¹⁸F) PET scan after the 90 day window with sponsor approval if the investigator does not recognize any significant medical changes.
- b. A follow-up phone call to the subject, or information where applicable, will be conducted within 2 or 3 business days of each imaging day, but not before 48 hours post-injection, to confirm subject well-being and to collect information about any new adverse events. If both of these days are not business days, the follow-up phone call can occur the following business day.
- c. ECG (with results reviewed prior to flortaucipir (¹⁸F) administration).
- d. Subjects will receive a single IV bolus injection target dose of 370 MBq (10 mCi) of flortaucipir (¹⁸F) injection followed by a saline flush.
- e. At approximately 75 minutes following flortaucipir (¹⁸F) injection, a continuous 30-minute brain scan will begin.
- f. Or a licensed/credentialed medical professional (i.e. PET technologist, imaging center nurse or a regional equivalent) designated by the site principal investigator. If a designee performs this activity, the physician must be available to provide medical consultation.
- g. Or physician designee.
- h. Serum pregnancy test
- i. Urine pregnancy test prior to flortaucipir (¹⁸F) injection

6.2 Time Point Algorithms

6.2.1 Windows

For all analyses, results will be summarized at the planned study visit they were obtained.

6.3 Screening and Baseline Assessments

Screening assessments took place over several days, within 90 days of the flortaucipir PET scan, and included demographics, medical history and concomitant medications, a physical exam, and a safety evaluation. Additionally, participants had an electrocardiogram (ECG) with results reviewed prior to the initial flortaucipir imaging visit.

6.4 Efficacy Variables

6.4.1 Primary Efficacy Variable(s)

6.4.1.1 Tau Status Based on Flortaucipir

The ¹⁸F-AV-1451 PET scan image was visually interpreted according to the following criteria:

Read Outcome		Objective Image Features
Not consistent with AD pattern (τAD-)		No increased neocortical activity, or increased neocortical activity isolated to the mesial temporal, anterolateral temporal, and/or frontal regions.
AD pattern (τAD)	τAD+	In either hemisphere, increased neocortical activity in the posterolateral temporal (PLT) or occipital region(s).
	τAD++	In either hemisphere, increased neocortical activity in the parietal/precuneus region(s), or frontal region(s) with increased uptake in the PLT, parietal, or occipital region(s).

6.4.1.2 Flortaucipir Quantitation

Standard uptake value ratios (SUVR) were calculated to estimate tau load globally and in individual regions for the flortaucipir images. A target region derived statistically with a Multiblock Barycentric Discriminant Analysis (MUBADA) method will be used for the global measurement.

Voxels of interest determined in the automated anatomical labeling (AAL) atlas masked to exclude white matter and CSF for amygdala, anterior fusiform, posterior fusiform, anterior hippocampus, posterior hippocampus, anterior parahippocampus, posterior parahippocampus, caudate, frontal, parietal, precuneus, temporal, occipital, left frontal, right frontal, left occipital, right occipital, left parietal, right parietal, left putamen, right putamen, left temporal, right temporal will be applied at the individual region level. A

selected white matter region derived using a parametric estimated signal reference intensity (PERSI) method will be used as reference region for all SUVr calculations.

MUBADA SUVr will be the variable used in any efficacy analysis involving flortaucipir quantitation. All regional SUVrs will be presented in listings.

6.4.1.3 Amyloid Status

A β is thought to accumulate very early in the AD process and is frequently observed in elderly subjects with no clinical symptoms. Furthermore, as a biomarker, A β plaques as seen on PET amyloid imaging appear to plateau in intensity early in the symptomatic phase of the disease. Amyloid positivity (A β ⁺ or A β ⁻) was determined by an Avid expert reader's visual interpretation.

6.4.2 Additional Efficacy Variables

6.4.2.1 Cognitive Assessments

Mini-Mental State Examination (MMSE)

The MMSE (Folstein et al., 1975) is a brief instrument used to assess cognitive function in elderly patients. The range for the total MMSE score is 0 to 30, the sum of each correct answer, with higher scores indicating better cognition. The score on a continuous scale will be used for primary objective analysis.

MMSE was recorded in the BIOCARD data. The MMSE measurement collected closest to the flortaucipir scan will be used for the purposes of the correlation analysis.

6.4.2.2 Functional Assessments

Pfeffer Functional Activities Questionnaire (FAQ), (Pfeffer et al. 1982)

Functional status is conceptualized as the “ability to perform self-care, self-maintenance and physical activities.” The FAQ was developed to assess instrumental activities of daily living involving higher level functional skills such as shopping alone, writing checks, remembering appointments, etc. The FAQ asks the informant to rate the patient's ability using the following scoring system: Dependent = 3; Requires assistance = 2; Has difficulty but does by self = 1; Normal = 0; Never did [the activity] but could do now = 0; Never did and would have difficulty now = 1. The sum scores ranges from 0-30, where higher scores indicate greater functional impairment. FAQ sum score will be used as a continuous variable in the primary objective analysis.

FAQ was recorded in the BIOCARD data. The FAQ measurement collected closest to the flortaucipir scan will be used for the purposes of the correlation analysis.

6.5 Drug Concentration Measurements and Pharmacokinetic Parameters

6.5.1 Handling of Pharmacokinetic Parameter Outliers

No pharmacokinetic parameters or drug concentration measurements will be collected during this study.

6.6 Safety Assessments

6.6.1 Extent of Exposure and Compliance to Study Treatment

During the flortaucipir imaging sessions, all subjects received a single IV bolus administration target dose of 370 MBq (10 mCi) of flortaucipir injection.

All exposure information will be summarized in a table and presented in a listing.

6.6.1.1 Unit Conversion for Radioactive Dose

All exposure tables and listings will display volume in MBq. Volume collected in mCi will be converted to MBq as follows:

$$MBq = 37 \times mCi$$

6.6.2 Adverse Events

An AE is any undesirable experience occurring to a subject during a clinical trial, whether or not considered related to the study drug. AEs are classed by severity and seriousness.

Treatment-emergent adverse events (TEAE) are any untoward medical occurrences associated with the use of a drug in humans, whether or not considered drug related. For the purposes of this study, untoward medical occurrences will be considered associated with the use of flortaucipir, and thus be reported as TEAEs if they occur within 48 hours after administration of the PET tracer. The end of study for the purpose of AE reporting is defined as 48 hours after the administration of flortaucipir injection.

The investigator's verbatim term of both serious and non-AEs will be mapped to system organ class (SOC) and preferred terms (PT) using the Medical Dictionary for Regulatory Activities (MedDRA) Version 19.1.

Severity is classified as mild/moderate/severe (increasing severity). If a subject reports a TEAE more than once within that SOC/PT, the TEAE with the worst case severity will be used in the corresponding severity summaries.

Serious AEs (SAEs) are events that result in one of the following outcomes or constitute one of the following events:

- Death

- Initial or prolonged hospitalization (other than that required by protocol; “social hospitalization” or any hospitalization for non-medical reasons does not constitute an SAE)
- A life-threatening experience (that is, immediate risk of dying)
- Persistent or significant disability/incapacity
- Congenital anomaly/birth defect
- Considered significant by the investigator for any other reason

7 STATISTICAL METHODS

7.1 Definitions and Conventions

All analysis will be performed using SAS version 9.2 or higher.

Data will be summarized using descriptive statistics (number of subjects [n], mean, standard deviation [SD], median, minimum [min], and maximum [max]) for continuous variables and using frequency count and percentage for discrete variables. Percentages will be rounded to one decimal place, except 100% will be displayed without any decimal places and percentages will not be displayed for zero counts.

The tables and listings will be numbered using a decimal system to reflect main levels of unique tables and listings and sub-levels of replicate tables and the listings with maximum two digits per level (e.g., Table XX.YY.ZZ...). Tables will be presented in clinical study report (CSR) section 14, and thus will be numbered as 14.YY.ZZ. Baseline analysis will be reported in table series 14.1, efficacy analysis in series 14.2, and safety analysis in series 14.3. Listings will be presented in in CSR section 16, and thus will be numbered as 16.YY.ZZ.

Unless otherwise specified, hypothesis testing will be two-sided with type I error rate of 0.05.

7.2 Handling of Dropouts or Missing Data

Dropout subjects will not be replaced in this study. For situations with no rules for handling missing data the default will be no imputation.

7.3 Interim Analyses and Data Monitoring

No interim analysis or data monitoring is planned for this study.

7.4 Multi-center Studies and Pooling of Centers

This is a single center study. The pooled data will be analyzed and presented.

7.5 Multiple Comparisons/Multiplicity

No multiple comparisons/multiplicity adjustment is planned.

7.6 Examination of Subgroups

No subgroup analysis will be conducted for this study.

8 STATISTICAL ANALYSIS

8.1 Analysis Populations

8.1.1 Enrolled Population

The enrolled population will consist of all BIOCARD study subjects who have signed the consent form for AV-1451-A20 and data exists in the electronic data capture system set for this AV-1451-A20. Disposition will be summarized using the enrolled population.

8.1.2 Safety Population

The safety population will consist of all subjects who received at least one injection of flortaucipir. All baseline and safety data will be summarized and listed using the safety population. All efficacy variables described in section 6.4 will be presented in listings for the safety population.

8.1.3 Efficacy Population

The efficacy population will include all subjects with a valid, interpretable baseline PET image (visual read and/or SUVr). All efficacy endpoints will be summarized using the efficacy population.

8.2 Disposition and Withdraws

The enrolled population will be represented in the disposition table. The disposition table will summarize the analysis populations in section 8.1, completed, and discontinued subjects.

Discontinued subjects will be defined as any safety subject who fail to complete the 24-48 hour safety follow-up. Termination status (i.e. 'Completed' and 'Discontinued') percentages will be based on the safety population. Percentages outlining discontinuation reasons will be based on the number of discontinued subjects.

8.3 Baseline Subject Data

8.3.1 Demographic and Other Baseline Characteristics

All baseline summaries will be based on the safety population. Age (years), gender, race, ethnicity, education, ApoE genotyping, alcohol, drug use, and smoking will all be summarized in a table and presented in a listing.

8.3.2 Medical and Surgical History

Medical and surgical histories were coded using MedDRA version 19.1, and will be presented in a listing for the safety population.

8.3.3 Concomitant Therapy

Concomitant therapies were coded using WHODRUG 3Q 2016. All concomitant medications data will be presented in listing.

8.3.4 Pregnancy Test

Pregnancy testing information captured on the case report form (CRF) will be presented in a listing for the safety population.

8.3.5 Electrocardiogram

ECG data captured on the CRF will be presented in a listing for the safety population.

8.4 Analysis of Efficacy Parameters

8.4.1 Analysis of Primary Efficacy Variable

8.4.1.1 Qualitative Assessment of Images

The visual read results as described in section 6.4.1.1 will be summarized for the efficacy population using descriptive statistics by amyloid status (A β +, A β -) in a 2x3 table.

8.4.1.2 Quantitative Assessment of Images

The MUBADA SUVR as described in section 6.4.1.2 will be summarized for the efficacy population using descriptive statistics by amyloid status (A β +, A β -).

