**CONFIDENTIAL**

This material is the property of Avid Radiopharmaceuticals (Avid). The information is confidential and is to be used only in connection with matters authorized by Avid and no part of it is to be disclosed to others without prior written permission from Avid.

Sponsor: Avid Radiopharmaceuticals
	
Name of Compound: flortaucipir (F) Injection
	
Active Ingredient(s): 7-(6-[F-]fluoropyridin-3-yl)-5H-pyrido[4,3-b]indole

Title of Study: “Flortaucipir (F) PET Imaging in the BIOCARD Study”
		

Planned number of subjects (Enrolled): Approximately 100
 
Subjects will be recruited from the pool of participants in the Biomarkers of Cognitive Decline Among Normal Individuals study (BIOCARD) being conducted at Johns Hopkins University. The overall recruitment goal is that 80 percent of subjects are amyloid positive, and 20 percent are amyloid negative.
		

Name of compound: flortaucipir (F) Injection (also known as F-AV-1451)  Dose: 370 MBq (10 mCi)  Route of Administration: Intravenous (IV) bolus
		

Study Phase: I
		

Study Centers: 1 center in the United States
		

Trial Objectives:
 
The primary objectives of this study are:
 
 
• To evaluate imaging characteristics of flortaucipir (F) in respect to brain amyloid status in subjects who are enrolled in the BIOCARD study
 
• To examine the relationship between cognitive and functional performance, other biomarker data, and tau deposition as measured by flortaucipir (F) uptake in clinically normal subjects
 
 
A secondary objective of this study is:
 
 
• To expand the flortaucipir (F) safety database.
 
		

Eligibility:
 
Only subjects duly consented and enrolled in the BIOCARD protocol (conducted by Johns Hopkins University with [name] as Principal Investigator) will be considered for participation in this study (see Section 5.3, Selection of Subjects).
		

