## 2. TRIAL OBJECTIVES

The primary objectives of this study are:

- To evaluate imaging characteristics of flortaucipir ( $^{18}\text{F}$ ) in respect to brain amyloid status in subjects who are enrolled in the BIOCARD study
- To examine the relationship between cognitive and functional performance, other biomarker data, and tau deposition as measured by flortaucipir ( $^{18}\text{F}$ ) uptake in clinically normal subjects

A secondary objective of this study is:

[figure not shown]
- To expand the flortaucipir ( $^{18}\text{F}$ ) safety database.

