### **5. INVESTIGATIONAL PLAN**

#### **5.1 Overall Design and Plan of Trial**

This is a phase I study that will evaluate imaging characteristics of flortaucipir ( $^{18}\text{F}$ ) in subjects enrolled in the BIOCARD study.

Subjects enrolled in the BIOCARD study will be contacted to participate and must provide informed consent before starting any AV-1451-A20 study procedures. In addition to consenting to study procedures, participants will consent to have BIOCARD-related data, including Magnetic Resonance Imaging (MRI) images/data, laboratory data, medical and neuropsychological assessments, as well as amyloid status, and lumbar puncture results, made available to this study to allow for analysis and comparison. This study hopes to recruit roughly 80 percent amyloid positive subjects, and 20 percent amyloid negative subjects from the BIOCARD study. Amyloid positivity will be determined by quantification of the BIOCARD PiB scan, and a list of patients for recruitment blinded to amyloid status will be provided to the site. Subjects' amyloid status will not be revealed as a part of recruitment or inclusion for this study.

Screening assessments may take place over several days, within 90 days of the flortaucipir ( $^{18}\text{F}$ ) Positron Emission Tomography (PET) scan, and will include demographics, medical history and concomitant medications, a physical exam, and a safety evaluation. Additionally, participants will have an ECG with results reviewed prior to the initial flortaucipir ( $^{18}\text{F}$ ) imaging visit. If the ECG was

performed within the last six to twelve months of the  $^{18}\text{F}$ -AV-1451 PET Imaging Visit and is available for review, the ECG does not need to be repeated. Subjects may be permitted to return for the flortaucipir ( $^{18}\text{F}$ ) PET scan after the 90 day window with sponsor approval if the investigator does not recognize any significant medical changes.

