2 INTRODUCTION

Of the 2 pathological protein deposits that are the hallmark of Alzheimer's disease (AD), beta- amyloid (A β) is thought to accumulate very early in the disease process and is frequently observed in elderly subjects with no clinical symptoms, a condition that may represent a preclinical phase of the disease. Furthermore, as a biomarker, A β plaques as seen on PET amyloid imaging appear to plateau in intensity early in the symptomatic phase of the disease.

In contrast to A β deposits, the density and distribution in the brain of phosphorylated tau, in the form of neocortical tangle pathology, has been shown in autopsy studies to be increased with AD-related cognitive impairment and appears to correlate with overall evidence of neurodegeneration across the entire spectrum of the illness (Duyckaerts et al. 1987; Nelson et al. 2012). Thus, an understanding of the onset and progression of tau pathology in relation to amyloid pathology and cognitive change may be critical to understanding the course of the disease.

It is important to evaluate cognitive normal subjects with elevated brain amyloid to obtain information regarding the presence/onset of tau pathology because clinically normal amyloid positive subjects have been hypothesized to represent the earliest preclinical stage of AD (Sperling et al., 2011). The present study planned to obtain flortaucipir (¹⁸F) tau positron emission tomography (PET) scans in up to 100 clinically normal subjects from the Biomarkers of Cognitive Decline Among Normal Individuals (BIOCARD) study that have been identified as having elevated brain amyloid by PET or cerebrospinal fluid (CSF) assays.

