4.3 Blinding

The study recruited roughly 80 percent Aβ+ subjects and 20 percent Aβ- subjects from the BIOCARD study. Amyloid positivity was determined by an Avid expert reader's visual interpretation. A list of subjects for recruitment was randomly selected, stratifying by amyloid status to maintain an approximately 80% Aβ+ subjects. The list was provided to the site with amyloid status blinded. The subjects' amyloid status were not revealed as a part of recruitment or inclusion for this study.

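### The SAP relates tau uptake to amyloid only by a two-level visual-read status, so the other-biomarker part of primary objective 2 has no amyloid-burden analysis

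*SAP*

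**What the plan says.** Objective 1 (Protocol section 2; SAP section 3 is nearly identical) is to evaluate the imaging characteristics of flortaucipir "in respect to brain amyloid status in subjects who are enrolled in the BIOCARD study". Objective 2, also primary, covers the relationship between tau uptake and cognitive and functional performance and other biomarker data in clinically normal subjects. Protocol 8.4 adds that the analyses will explore whether uptake is correlated with other biomarkers.

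The SAP relates tau to amyloid in two places:
- 8.4.1.1: the visual tau read "will be summarized for the efficacy population using descriptive statistics by amyloid status", as a 2x3 table.
- 8.4.1.2: "The MUBADA SUVR as described in section 6.4.1.2 will be summarized for the efficacy population using descriptive statistics by amyloid status".

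The two planned correlations (8.4.1.3 and 8.4.1.4) are of MUBADA SUVr with MMSE and with FAQ.

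Protocol 5.1 states: "Amyloid positivity will be determined by quantification of the BIOCARD PiB scan". In the SAP (4.1, 4.3, 6.4.1.3) positivity instead comes from a visual read, and section 6.4 defines no PiB quantity.

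On numbers, the protocol synopsis gives "Planned number of subjects (Enrolled): Approximately 100", while SAP 4.4 reports: "Twenty-three (23) subjects were dosed with flortaucipir and had an accompanying visual read or imaging quantification". The recruitment list was drawn at random, "stratifying by amyloid status to maintain an approximately 80" percent positive (SAP 4.3).

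**The concern.** The study's rationale is the onset of tau pathology in clinically normal people with elevated amyloid. The SAP introduction says that amyloid plaques on PET "appear to plateau in intensity early in the symptomatic phase of the disease". If so, burden should still vary among clinically normal subjects. A two-level status treats all positives as alike, and on the recruitment target they are about four fifths of the sample. The planned tables therefore cannot show whether uptake rises with amyloid burden. The comparison that they do show rests on a small negative group.

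The gap lies under objective 2 and Protocol 8.4. Both call for relating uptake to other biomarkers, and the SAP turns neither into an analysis. A quantitative PiB value is an obvious candidate, because the protocol already describes deriving one.

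**Working it through.** SAP 4.4 says that no power or sample-size calculation was done, so there is no planned figure to reproduce. The documents give no SD, no tau-amyloid correlation and no PiB distribution. Results are therefore in SD units or rest on stated assumptions.

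**1. Expected group sizes.** 0.20 × 23 = 4.6, so about 5 negatives and 18 positives. This comes from a target and is not a count. The efficacy population (SAP 8.1.3) accepts a visual read without an SUVr, so the number with an SUVr could be below 23.

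**2. Precision of a by-status difference in mean SUVr.** Half-width = t(0.975, n₁+n₂−2) × √(1/n₁ + 1/n₂), in SD.

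| Positive v negative | √(1/n₁ + 1/n₂) | 95% half-width |
|---|---|---|
| 18 v 5 | 0.506 | 2.080 × 0.506 = 1.05 SD |
| 19 v 4 | 0.550 | 2.080 × 0.550 = 1.14 SD |
| 80 v 20 (original target size) | 0.250 | 1.984 × 0.250 = 0.50 SD |

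**3. Information kept by status.** The measure is the squared correlation between the two-level status and the continuous value, under three assumed shapes.

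- *Normal value cut within the sample.* Kept = φ(z_p)² / [p(1−p)]. At p = 5/23: 0.294² / (0.2174 × 0.7826) = 0.0865 / 0.1701 = 0.51. At p = 0.20: 0.280² / 0.16 = 0.49.
- *Stratified draw of 18 and 5 from a normal pool with 30% positive.* This is closest to SAP 4.3, but the 30% is assumed. The positive and negative means are 0.348/0.30 = 1.159 and −0.348/0.70 = −0.497, and the within-group variances are 0.265 and 0.493. Between groups: 0.1701 × 1.656² = 0.466. Within groups: 0.7826 × 0.265 + 0.2174 × 0.493 = 0.314. Kept = 0.466 / 0.780 = 0.60 in large samples, and about 0.62 averaged over simulated samples of 23. Pools with 20% to 40% positive give 0.64 to 0.57.
- *Bimodal value.* Take group means d apart, in SDs of the positive group, with negative-group SD 0.3. Kept = 0.1701d² / (0.1701d² + 0.802). For d = 2, 3 and 4 this is 0.46, 0.66 and 0.77.

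The overall range is 46% to 77% kept, so roughly a quarter to just over a half is lost.

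**4. What a slope would add.** This uses the stratified model with a 30% positive pool, 18 and 5 subjects, and two-sided 0.05. Power serves only as a yardstick. At an assumed pool correlation of 0.5, a linear slope on the continuous value has about 61% power, against 40% for a t-test by status. At 0.6 it is about 81% against 58%.

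**5. Within the positives only.** Restricting the range weakens the correlation. At 0.5 in the pool it becomes 0.5√0.265 / √(0.25 × 0.265 + 0.75) = 0.257 / 0.903 = 0.28. With 18 subjects, power is about 17% (Spearman) to 22% (Pearson).

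**The case against.** The strongest reply is that the SAP analyses what objective 1 asks. That objective is worded as amyloid status, and 8.4.1.1 and 8.4.1.2 summarise both tau measures by status. This stands, and the by-status tables should stay.

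A reader might infer that the SAP discards a PiB variable that the protocol planned to analyse. The documents do not support that. The protocol uses quantification to classify subjects and nowhere names a PiB value as an analysis variable. Following it to the letter would still give two groups under objective 1. The SAP then relies on a visual read, so it is not documented that a quantitative value is in hand for the 23 subjects. The addition must be conditional on that.

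A reader might also infer lost power for a planned test. No test is specified for objective 1, and the SAP calls the study exploratory. What is lost is descriptive precision and any view of a graded relation.

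Finally, the added analysis will say little about the positives alone (step 5 of the working). That also stands. Much of the whole-sample gain comes with the contrast between positives and negatives.

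None of this meets the remaining gap: objective 2 and Protocol 8.4 call for biomarker relationships, and the SAP provides none.

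**Conclusion.** The point holds as a missing analysis under objective 2 and Protocol 8.4. The by-status summaries are valid for objective 1.

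At an inferred 18 against 5, a mean SUVr difference would be known only to about ±1.05 SD. Status keeps roughly 46% to 77% of the information in a continuous amyloid value, and about 62% under a stratified draw from a pool assumed 30% positive. A flat statement that half is lost would be too strong: it needs a normal PiB value cut within the sample, which ignores the stratified selection.

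The conclusion rests on three assumptions: that the achieved split is near the target, that the PiB distribution lies within the shapes tried, and that quantitative PiB values exist or can be derived. A material loss appears under every shape tried; its exact size cannot be fixed from the documents.

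**What to change.** Keep 8.4.1.1 and 8.4.1.2, and report the number of positive and negative subjects behind each summary. Then add to SAP 8.4, for subjects with a quantitative PiB value:

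- a linear regression of MUBADA SUVr on that value, reporting the slope with its 95% CI and the number of subjects included;
- a scatter plot of the two, with points marked by visual amyloid status;
- the slope within amyloid-positive subjects with its CI, labelled descriptive only because it will be imprecise.

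Define the PiB quantity in SAP 6.4. Regression of tau on amyloid suits this sample, because selecting subjects on the predictor does not by itself bias a correctly specified slope. An overall correlation coefficient is affected by that selection. If one is shown, state that it describes the amyloid-enriched sample and not BIOCARD as a whole.

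The cost is a short SAP addition and one figure if the values have already been transferred. If not, they must be obtained from the existing BIOCARD scans. Subjects without a PiB value drop out of the added analysis but remain in the by-status summaries.
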